Secondary objective: 
Compare magnitude of tracer-derived biochemical uptake measure with tumour grade.
Tertiary objective: 
Compare magnitude of tracer-derived biochemical uptake measure with ex vivo gene expression specifically for metabolism.Compare magnitude of tracer-derived biochemical uptake measure with ex vivo tissue metabolite analysis using Mass Spectrometry (MS).Compare the magnitude of tracer-derived biochemical uptake measure with ex vivo protein and phosphoprotein analysis from the major cell proliferation and survival pathways including phospho ERK 1/2 and pSer641.Comparison of flux constants derived from mathematical modelling of ^{18}F-FPIA PET/MRI data with tumour grade.Comparison of tracer-derived biochemical uptake measure with conventional MRI variables including perfusion imaging and contrast enhancement.
Study Design: Primary Endpoint: 
Quantitative measurement of ^{18}F-FPIA uptake in human gliomas.

Secondary endpoint:

- Correlation of ¹⁸F-FPIA uptake with tumour type and histological grade including O⁶-methylguanine-DNA methyltransferase (MGMT) and isocitrate dehydrogenase (IDH) gene expression.

Tertiary endpoint:

- Correlation of ¹⁸F-FPIA uptake with expression of genes responsible for metabolism on tissue obtained after surgery.
- Correlation of ¹⁸F-FPIA uptake with tissue metabolites obtained after surgery.
- Correlation of ¹⁸F-FPIA uptake with tissue proteins and phosphoproteins obtained after surgery.
- Correlation of ¹⁸F-FPIA flux constants with histological grade.
- Correlation of ¹⁸F-FPIA variables with structural and functional MRI variables including perfusion.

Selection of Subjects:**Inclusion Criteria:**

Patients with radiological evidence of suspected cerebral glioma due for surgery or biopsy and with the following characteristics will be recruited:

1. Age \geq 18
2. Tumour size at least 2 cm.
3. WHO performance status 0 – 2.
4. If female, the subject is either post-menopausal (at least 1 year), or surgically sterilized (has had a documented bilateral oophorectomy and/or documented hysterectomy for at least 2 years,), or if of childbearing potential, must have a negative urine beta human chorionic gonadotropin (β -HCG) pregnancy test done at initial screening and on the day of tracer administration. The result of the pregnancy test must be known before administration of ¹⁸F-FPIA injection.
5. The subject is able and willing to comply with study procedures, and signed and dated informed consent is obtained.
6. The subject has a satisfactory medical history as judged by the investigator with no significant co-morbidities, physical examination, and vital signs findings during the screening period (from 21 days before administration).
7. The subject's clinical and laboratory tests are within normal limits and/or considered clinically insignificant.

Exclusion Criteria:

8. The subject has received any chemotherapy, immunotherapy, biologic therapy or investigational therapy within 14 days or five half-lives of a drug (whichever is longer) prior to the first dose of ¹⁸F-FPIA injection. The subject is pregnant or lactating.
9. The subject is diabetic or has uncontrolled blood glucose or blood lipid levels (clinical decision by investigator), any other chronic illness that will preclude brief discontinuation of medication, or musculoskeletal condition that would not allow comfortable performance of a 66-minute study.
10. The subject has received another investigational radioactive tracer within 1 month before administration of ¹⁸F-FPIA injection.
11. Anticoagulation therapy, prolonged prothrombin time, abnormal Allen's test.
12. Unsatisfactory renal function (eGFR<60)

Number of Patients Planned: 10

- In the event of unevaluable data, additional patients will be recruited to reach a total number of 10 complete patients.

Treatment of Subjects: Experimental imaging biomarker tracer:

- Subjects will receive a single I.V. bolus injection of ¹⁸F-FPIA over a period of about 30 seconds. The tracer injection will be followed by a saline flush. Patients will receive a maximum ¹⁸F activity of 370 MBq.

Statistical Methods and Planned Analysis:

- The study is an Observational Non-randomised Phase 2 study to determine the magnitude of the early steps of fatty acid oxidation in glioma using ¹⁸F-FPIA PET/MRI. This is the first time we are using FPIA in patients (with glioma), thus we do not know *a priori* the magnitude of uptake. Statistical tests will use a 0.05 significance level and will be 2-sided unless otherwise noted. 10 evaluable patients will be recruited for the study with the Upper Confidence Interval of sensitivity to detect fatty acid metabolism set to $\geq 90\%$. All patients will undergo surgical resection or biopsy for histological confirmation of tumour grade.

TABLE OF CONTENTS

- 1. SYNOPSIS**

2. LIST OF ABBREVIATIONS AND DEFINITION OF TERMS

AE	Adverse event
ARSAC	Administration of Radioactive Substances Advisory Committee
CT	Computed Tomography
ED	Effective Dose (i.e., the sum of risk weighted organ absorbed radiation dose used as a measure of stochastic radiation risk)
EC	Ethics committee
FDG	¹⁸ F – fluorodeoxyglucose
¹⁸ F	Fluorine with an Atomic Mass of 18
¹⁸ F-FPIA	¹⁸ F-fluoropivalate (¹⁸ F-fluoro-2,2-dimethylpropionic acid)
GCP	Good Clinical Practice
GLP	Good Laboratory Practice
GMP	Good Manufacturing Practice
i.v	Intravenous
MBq	Megabecquerel
PET	Positron emission tomography
SAE	Serious adverse event
SUV	Standardized uptake value
MRI	Magnetic resonance imaging
NMR	Nuclear magnetic resonance
MS	Mass spectroscopy
TR	Time to repeat
TE	Time to echo

IDH	Isocitrate dehydrogenase
MGMT	O6-methyl-guanly-methyl-transferase
LCMS	Liquid chromatography mass spectroscopy
eGFR	Estimated glomerular filtration rate

3. BACKGROUND

Glioma is the most common primary malignant brain tumour in adults and has an extremely poor prognosis. The two-year survival rate is a mere 26.5% for Glioblastoma (GBM), its most aggressive form despite treatment with radiotherapy and temozolomide. [1].

Gliomas like other tumours were originally thought to primarily metabolise glucose for energy production, however the reliance on glycolysis has recently been called into question. Lin et al. demonstrated that cells derived from human glioma, when cultured under optimal conditions expressed fatty acid oxidation enzymes and were dependent upon fatty acid oxidation for aerobic respiration and proliferation [2]. These findings were consistent with preclinical studies in which treatment of mice with etomoxir, an inhibitor of fatty acid oxidation demonstrated significantly reduced tumour growth and increased survival time [2]. Very recent work indicates a striking common metabolic phenotype of GBM and brain metastases to simultaneously oxidise acetate and glucose [3]. This adaptation may be important for meeting the high biosynthetic and bioenergetic demands of malignant growth. Furthermore, it has been shown that the key gene responsible for this phenotype, ACSS2, permits cells to exist under bioenergetic stress, which is a potential adaptation to therapy resistance [4]. Tumour cells, including brain tumour cells efficiently oxidize fatty acids synthesized from acetate to generate a substantial part of the cell's ATP requirement, as well as NADPH to buffer reactive oxygen species.

There is currently no method for quantifying tissue fatty acid oxidation in humans. Our group has characterized ^{18}F -fluoropivalate (^{18}F -FPIA; 3- ^{18}F -fluoro-2,2-dimethylpropionic acid) as a tracer to report the early steps of fatty acid oxidation in non-clinical studies using PET imaging [4] [5]. ^{18}F -FPIA shows high contrast for imaging brain tumour xenografts implanted subcutaneously in mice [5], and orthotopically in the brain (unpublished) with the magnitude of tumour uptake equivalent to that of conventional tracers such as FDG but with significantly lower normal brain uptake giving a high signal to noise ratio enabling its use as suitable surrogate biomarker for fatty acid oxidation. Our current objective is to quantify the magnitude of early step fatty acid oxidation in human gliomas thought to possess enhanced fatty acid oxidation [3].

Combined hybrid PET/MRI technology permits simultaneous acquisition of PET imaging with conventional MRI sequences including T1, T2/FLAIR (with and without contrast) and perfusion (DSC-MRI). Patients with Glioma will all undergo routine biopsy or surgery following imaging and so we will have the opportunity to correlate the degree of fatty acid oxidation with tumour grade and genes involved in metabolism. Further tissue analysis will involve liquid chromatography mass spectroscopy-metabolomics, protein, and phospho-protein analysis. Mathematical modelling of tissue and blood data will be conducted to permit derivation of flux constants describing delivery and retention of the radiotracer.

4. RATIONALE FOR CURRENT STUDY

4.1 Aim:

The aim of this study is to quantify the degree of early step fatty acid oxidation in gliomas as imaged by ^{18}F -FPIA PET/MRI.

4.2 Hypothesis:

We hypothesise that FPIA uptake will be higher in high-grade gliomas compared to lower grade gliomas, in keeping with a higher propensity of high grade tumours to generate ATP and NADPH via fatty acid oxidation under bioenergetic stress.

4.3 Statistical Design:

The study is an Observational Non-randomised Phase 2 study to determine the magnitude of the early steps of fatty acid oxidation in glioma using ^{18}F -FPIA PET/MRI. This is the first time we are using FPIA in patients (with glioma), thus we do not know *a priori* the magnitude of uptake. Statistical tests will use a 0.05 significance level and will be 2-sided unless otherwise noted. 10 evaluable patients will be recruited for the study with the Upper Confidence Interval of sensitivity to detect fatty acid metabolism set to $\geq 90\%$. All patients will undergo surgical resection or biopsy for histological confirmation of tumour grade.

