5. STUDY OBJECTIVES AND ENDPOINTS

5.1 Primary Objective:

- Determine the magnitude of the early steps of fatty acid oxidation in glioma using ^{18}F -FPIA PET/MRI.

5.2 Secondary objective:

- Compare magnitude of tracer-derived biochemical uptake measure with tumour grade.

5.3 Tertiary objective:

- Compare magnitude of tracer-derived biochemical uptake measure with ex vivo gene expression specifically for metabolism.
- Compare magnitude of tracer-derived biochemical uptake measure with ex vivo tissue metabolite analysis using Mass Spectrometry (MS).
- Compare the magnitude of tracer-derived biochemical uptake measure with ex vivo protein and phosphoprotein analysis from the major cell proliferation and survival pathways including phospho ERK 1/2 and pSer641.
- Comparison of flux constants derived from mathematical modelling of ^{18}F -FPIA PET/MRI data with tumour grade, contrast enhancement and perfusion.

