6. STUDY ENDPOINTS

6.1 Primary Endpoint:

- Quantitative measurement of ^{18}F -FPIA uptake in human gliomas.

6.2 Secondary endpoint:

- Correlation of ^{18}F -FPIA uptake with tumour type and histological grade including O⁶-methylguanine-DNA methyltransferase (MGMT) and isocitrate dehydrogenase (IDH) gene expression.

6.3 Tertiary endpoint:

Measuring fatty acid oxidation in gliomas using ^{18}F -FPIA Version 1.0_01/02/2018 IRAS: 228245

- Correlation of ¹⁸F-FPIA uptake with expression of genes responsible for metabolism on tissue obtained after surgery.
- Correlation of ¹⁸F-FPIA uptake with tissue metabolites obtained after surgery.
- Correlation of ¹⁸F-FPIA uptake with tissue proteins and phosphoproteins obtained after surgery.
- Correlation of ¹⁸F-FPIA flux constants with histological grade.
- Correlation of ¹⁸F-FPIA variables with structural and functional MRI variables including perfusion.

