9. COMPLETION, WITHDRAWAL AND TERMINATION CRITERIA

9.1 Subject completion

A completed subject is one who has completed all imaging sequences of the combined ^{18}F -FPIA PET/MRI protocol.

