11.6 Data Analysis

Raw PET dynamic attenuation corrected images will be reconstructed. Decay corrected images will then be viewed using Analyze[®], Hermes or other appropriate software. Next, the summed images from 15 min to 65 min will be obtained and regions of interest (ROI) will be drawn around the tumour and normal tissues to derive semi-quantitative uptake parameters: SUV (standardized uptake value) normalised to body weight (bw). The average and maximum SUV at 60 min (SUV_{60,av}, and SUV_{60,max}) will be calculated. Arterial blood samples counted for tracer activity and metabolites of ^{18}F -FPIA will be used to generate the blood input function used to derive the uptake tracer parameters (image derived input function *Measuring fatty acid oxidation in gliomas using ^{18}F -FPIA Version 1.0_01/02/2018 IRAS: 228245*

will also be used).

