11.9 Tissue Analysis

All patients enrolled into the study, will have their routine biopsy or surgery tissue made available for analysis. We will seek data from routine clinical tissue assays including MGMT, IDH-1 status used for confirming tumour grade.

Following this we will perform our own analysis on tissue including gene, protein, and phospho-protein analysis. Illumina RNA Seq method or similar will be used for gene expression analysis. An automated reverse-phase protein array (RPPA) platform offering detection of approximately 150-170 protein and phospho-proteins from the major cell proliferation and survival pathways (including phospho-ERK 1/2, GYS1-pSer641) will be employed for protein/phospho-protein analysis. Tumour tissue will be obtained for NMR and Mass Spectrometry metabolomics at the Imperial College Biomedical Research Centre (BRC) Clinical Phenome Centre.

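### The flat two-sided 0.05 level has no exception or multiplicity method for the tertiary molecular correlations; if each of about 150 to 170 array proteins is tested once, 7.5 to 8.5 are expected to pass by chance.

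*Combined protocol and SAP*

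**What the plan says.** Section 4.3, and the same text in the Synopsis under statistical methods, sets one rule for every test: "Statistical tests will use a 0.05 significance level and will be 2-sided unless otherwise noted".

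The tertiary endpoints in section 6.3 include the correlation of ¹⁸F-FPIA "uptake with tissue proteins and phosphoproteins obtained after surgery", of "uptake with expression of genes responsible for metabolism on tissue obtained after surgery" and of "uptake with tissue metabolites obtained after surgery". Section 11.9 describes the protein assay, a reverse-phase protein array (RPPA), as a "platform offering detection of approximately 150-170 protein and phospho-proteins". Gene expression is to be measured by RNA sequencing or a similar method, and metabolites by NMR and mass spectrometry. Neither has a stated number of markers.

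There is some focus. Section 5.3 limits the gene comparison to "ex vivo gene expression specifically for metabolism", and sections 5.3 and 11.9 name two phosphoproteins, but as examples within the panel and not as a closed list.

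The objectives, the endpoints and sections 11.6 to 11.10 give no different significance level, no multiplicity method and no statement that the tertiary correlations are descriptive only.

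**The concern.** The 0.05 rule is open to exceptions and none is made, so on its face it covers the molecular screens. One endpoint line, correlation of uptake with tissue proteins, can hold well over a hundred tests. Applied marker by marker, the rule yields a list of significant proteins even if uptake is related to none of them.

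What is at stake is how that list is read. A reader given only nominal p-values from 10 patients could not tell which proteins to follow up. The estimate of uptake in gliomas (primary) and its comparison with tumour type and grade (secondary) are not touched by this point.

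**Working it through.** The documents state no expected number of chance findings, so there is no figure of theirs to reproduce.

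**Inputs.** α = 0.05, two-sided (4.3, Synopsis). Markers m = 150 to 170 (11.9). Patients n = 10 (4.3). Assumption: each protein is tested once, against one uptake measure.

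**1. Expected chance passes.** If no marker is related to uptake, the expected number is m × α:
- 150 × 0.05 = 7.5
- 170 × 0.05 = 8.5

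This mean holds whether or not the proteins are correlated. It requires a test whose true size is 0.05, such as Pearson's correlation on normal data.

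**2. With a rank test.** The documents name no correlation coefficient. Spearman's coefficient takes discrete values at n = 10. The largest attainable two-sided size not above 0.05 is 0.0488 (|ρ| ≥ 0.648, from 2 million permutations):
- 150 × 0.0488 = 7.3
- 170 × 0.0488 = 8.3

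**3. Spread around the mean.** Simulation with 160 null markers, n = 10, Pearson on normal data. The inter-marker correlations are assumed.

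| Inter-marker correlation | Mean | Median | 5th to 95th percentile |
|---|---|---|---|
| 0 | 8.0 | 8 | 4 to 13 |
| 0.3 | 7.9 | 6 | 1 to 21 |
| 0.5 | 7.9 | 4 | 0 to about 30 |

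Repeating the simulation moved the upper percentiles by at most 3. The mean stays near 8, but the count becomes skewed and very variable as correlation rises.

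**4. What a nominal pass conveys.** With 8 degrees of freedom the critical t is 2.306, so the critical |r| = 2.306 / √(2.306² + 8) = 0.632. By Fisher's transformation, atanh(0.632) = 0.745 and 1.96/√7 = 0.741. The 95% interval on the z scale is 0.004 to 1.486, which is 0.004 to 0.902 as a correlation. A marker that just passes is compatible with almost no relation and with a very strong one.

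**5. What false-discovery control would do.** Assume 16 true correlates of r = 0.7 among 160 markers, n = 10. Results are simulation averages at inter-marker correlation 0 / 0.3 / 0.5.

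| Rule | True markers found | False markers found | Runs with none found |
|---|---|---|---|
| Unadjusted 0.05 | 10.8 / 10.9 / 10.9 | 7.2 / 7.3 / 7.4 | not tabulated |
| Benjamini-Hochberg, 5% | 2.2 / 2.5 / 2.7 | 0.2 / 0.3 / 0.6 | 43% / 50% / 56% |

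As a check, 144 null markers × 0.05 = 7.2 false passes. Under the unadjusted rule, false passes are then 7.2 / (10.8 + 7.2) = 40% of all passes on average, even with this generous share of strong true correlates.

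**The case against.** Four arguments run the other way.

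- **Marker-by-marker testing is inferred.** The 150 to 170 figure is what the array can detect, not a planned number of tests. Comparing and correlating, the words of sections 5.3 and 6.3, also fit pure estimation, and the only stated hypothesis (4.2) concerns grade. This stands as a condition: the count applies only if each protein is tested once. It remains a natural reading, because the 0.05 rule and the protein endpoint are both unrestricted.
- **The exploratory status is already visible.** The Synopsis classes the study as explorative, these endpoints sit in the third tier, and there are 10 patients. This limits the weight of the point. It does not lift the 0.05 rule or tell a reader how to treat nominal passes.
- **False-discovery control finds little at this size.** That is true, as step 5 shows. It would count against discarding markers that fail, but the change below discards none.
- **Conventions differ** on whether screens in so small a study need formal control. That supports treating this as optional.

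Some stronger readings are tempting and are not supported:

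- *About eight false proteins will appear in this study.* Eight is a mean. With correlated proteins the median is lower and the range wide.
- *The total across all platforms is far larger.* Gene and metabolite counts are not given, so no total can be stated.
- *Testing two uptake measures inflates the count further.* Section 11.6 says that "The average and maximum SUV at 60 min" will be calculated, not that both will be screened against every marker.
- *Fewer than 10 patients will have tissue results.* Section 9.1 defines completion by imaging ("A completed subject is one who has completed all imaging sequences of the combined"), but 11.9 expects tissue from all enrolled patients. Any lower number is an assumption.

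The unnamed uptake measure and coefficient, the unfixed gene and metabolite lists and the tissue count are missing detail. The multiplicity point does not depend on them.

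**Conclusion.** The point holds in a limited form. The plan's only rule on significance reaches the tertiary molecular correlations with no exception or multiplicity method. Read marker by marker, it gives an expected 7.5 to 8.5 chance passes on the protein array with an exact-size test, or about 7.3 to 8.3 with Spearman's test at n = 10, so nominal passes alone would not separate true correlates from chance.

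The expected count rests on one test per protein, one uptake measure and no true relation. The spread, and the yield under false-discovery control, rest on assumed inter-marker correlations, numbers of true correlates and effect sizes that the documents do not give. The consequence is confined to the reporting of tertiary, exploratory results. This is a cheap improvement that the sponsor could make, not a defect in the study's main analysis.

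**What to change.** Add to section 4.3 and the Synopsis, for example: *The tertiary molecular correlations are hypothesis-generating. The per-test 0.05 level will not be used to declare findings in them. Within each platform (protein array, metabolism genes, metabolomics), every marker tested will be reported as an estimate with its 95% confidence interval and Benjamini-Hochberg q-value, and the number of markers tested will be stated.*

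The cost is a few lines of text and trivial analysis time, with no extra patients, samples or assays. The downside is that with 10 patients the screens may yield few or no markers below a conventional q-value threshold; under the scenario in step 5 of the working, none in about 43% to 56% of runs. Because every estimate and interval is reported, markers that miss the threshold remain visible as candidates for later work.

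### The only stated basis for 10 patients is an upper confidence limit of sensitivity of at least 90%, which sets no minimum n and has no sensitivity measure in the plan to apply to

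*Combined protocol and SAP*

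**What the plan says.** Section 4.3 (Statistical Design) reads "10 evaluable patients will be recruited for the study with the Upper Confidence Interval of sensitivity to detect fatty acid metabolism set to" ≥90%, and the Synopsis repeats the sentence under Statistical Methods and Planned Analysis. Section 4.3 gives the general testing convention: "Statistical tests will use a 0.05 significance level and will be 2-sided unless otherwise noted". It explains the lack of an effect-size calculation by saying "thus we do not know *a priori* the magnitude of uptake". No confidence level, interval method, expected sensitivity, SD or power is given, and no other basis for 10 appears. Section 9.2 and the Synopsis add only that non-evaluable patients can be replaced to reach 10.

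The primary endpoint in section 6.1 is "Quantitative measurement of ^{18}F -FPIA uptake in human gliomas". Section 11.6 derives "The average and maximum SUV at 60 min" from regions drawn on tumour and normal tissue. Sensitivity does not appear among the objectives (section 5), the endpoints (section 6) or the analyses (sections 11.6 to 11.10). Section 4.2 hypothesises higher uptake in high-grade than in lower-grade glioma, with no expected difference or grade split.

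**The concern.** A confidence-limit target supports a sample size when it bounds the result from the unfavourable side: a lower limit that must exceed some value, or an interval no wider than a stated width. Such targets become achievable only as n grows. An upper limit that must reach 90% does the opposite, because wide intervals satisfy it and small samples give wide intervals.

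The target also refers to a quantity the study does not measure. Sensitivity needs a positive/negative reading and a reference standard, whereas the study measures continuous uptake.

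A reader may take the 90% figure as assurance about detection that 10 scans cannot give. Meanwhile the protocol does not say what 10 scans will deliver for mean uptake or for the grade hypothesis.

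**Working it through.** **Inputs.** n = 10 and the 90% upper limit come from section 4.3. The 95% level is an assumption suggested by the two-sided 0.05 convention there. The interval method and all true sensitivities below are also assumptions, shown as ranges.

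**1. Can the criterion reproduce n = 10?** No. With x = n detections the exact upper limit is 100% at every n, including n = 1, so no smallest n exists.

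**2. What passes at n = 10?** The exact (Clopper-Pearson) upper limit for x detections is the 0.975 quantile of Beta(x+1, n−x).

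| Method | Smallest passing count | Interval |
|---|---|---|
| 95% Wald | 6/10 | 29.6% to 90.4% |
| 95% exact | 7/10 | 34.8% to 93.3% |
| 95% Wilson | 8/10 | 49.0% to 94.3% |
| 80% exact | 8/10 | 55.0% to 94.5% |

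By the 95% exact method 6/10 just fails (upper limit 87.8%). A result that barely passes is compatible with a sensitivity as low as about 30% to 55%, depending on the method.

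The chance of passing is P(X ≥ threshold), with X binomial(10, p):

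| True sensitivity | Threshold 6 | Threshold 7 | Threshold 8 |
|---|---|---|---|
| 60% | 63% | 38% | 17% |
| 70% | 85% | 65% | 38% |

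**3. How does n affect it?** (95% exact)

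| n | Smallest pass | P(pass), true 70% | P(pass), true 90% |
|---|---|---|---|
| 5 | 3/5 | 84% | 99% |
| 10 | 7/10 | 65% | 99% |
| 20 | 15/20 | 42% | 99% |
| 40 | 32/40 | 11% | 98% |

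When true sensitivity is below 90%, the criterion is generally easier to meet with fewer patients. This is a trend; because counts are discrete it need not hold at every single step.

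**4. Was a lower limit meant?** If all n patients are positive, the exact lower limit is 0.025^(1/n) two-sided or 0.05^(1/n) one-sided.

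- n = 10: 0.025^(1/10) = 69.2%; 0.05^(1/10) = 74.1%. The 95% Wilson lower limit is 72.2%.
- To reach 90%: 0.025^(1/36) = 90.3%, so 36/36 two-sided; 0.05^(1/29) = 90.2%, so 29/29 one-sided.

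The Wald interval collapses to 100% to 100% when every patient is positive. It does so at every n, so it does not single out 10 either.

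**5. Can it be applied to the planned data?** Section 11.6 gives standardised uptake values but no threshold for a detection. Histology is used to confirm grade (section 4.3). The tissue assays in section 11.9 feed correlations (section 6.3) and are not named as a reference for the presence of fatty acid metabolism.

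**6. What does n = 10 deliver for the actual endpoint?**

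- Mean uptake: the 95% half-width is t(0.975, 9)/√10 = 2.262/3.162 = 0.72 sample SD.
- Difference in mean between grades: t(0.975, 8) × √(1/a + 1/b), with t = 2.306 and equal variances. This gives 1.46 within-grade SD for a 5:5 split, 1.59 for 7:3 and 1.82 for 8:2. The splits are assumptions.

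**The case against.** The strongest reply is that this is an exploratory, first-in-glioma study. Ten patients may be a reasonable number, no decision depends on the limit, and the uptake results would be reported identically with or without the clause. All of that stands. It confines the fault to the rationale, but it does not make the stated rationale support the number.

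A second reply is that a usable meaning can be guessed: tumour against normal tissue, in histologically confirmed glioma. The Background statement "There is currently no method for quantifying tissue fatty acid oxidation in humans" is there to motivate the tracer, so it is weak evidence that no reference could exist. That is fair, and the conclusion does not need it. What matters is that no cut-off and no reference standard are stated, and even with both supplied, step 1 still leaves no minimum n.

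A third reply concerns the precision figures. Patients are enrolled with suspected glioma (section 7.1) and completion is defined by imaging alone (section 9.1), so 10 evaluable patients may not be 10 gliomas. With 8, for illustration, the half-width would be t(0.975, 7)/√8 = 0.84 SD. Section 6.1 does not name the uptake measure, and section 11.8 adds kinetic parameters. The secondary endpoint is worded as a correlation, although section 4.2 and the objective in 5.2 both point to a comparison by grade. These points call for conditions on the replacement wording; they do not defend the sensitivity clause.

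**Conclusion.** The concern holds. The stated property does not lead to 10 patients under any of the interval methods tried, read as an upper or as a lower limit, and no planned analysis can check it. In size, a result as weak as 6/10 to 8/10 would satisfy it, and at an assumed true sensitivity of 70% it would be met 65% of the time at n = 10 (95% exact). The size figures depend on the assumed level and method. Two conclusions do not: detection in every patient meets the criterion at any n, and the plan defines no sensitivity outcome. This should be fixed, but it does not show that 10 is the wrong number for an exploratory study, and it does not invalidate the scans or the planned analyses.

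**What to change.** Delete the sensitivity clause in section 4.3 and in the Synopsis, and keep n = 10. In its place:

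- **Primary endpoint.** State that with 10 evaluable, confirmed gliomas the two-sided 95% confidence interval for mean SUV60,av (and likewise SUV60,max) has a half-width of about 0.72 sample SD, assuming approximate normality and pooling across grades, with the SD not known in advance. If another uptake measure is primary, name it instead.
- **Grade hypothesis (4.2).** State that the half-width for the difference in mean between high and lower grade is about 1.5 within-grade SD with a 5:5 split and 1.8 with 8:2, assuming equal variances.
- **Feasibility.** If feasibility set the number, say so.
- **Optional detection rate.** If one is to be reported, define detection before the data are seen, call it a detection rate in glioma, and give the exact two-sided 95% interval including its lower limit (for example 10/10: 69% to 100%; 7/10: 35% to 93%).

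The cost is wording in two places, with no extra patients or scans. The intervals use data already planned. The drawback is that the protocol will show wide intervals where it now shows a 90% figure.
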